Work-package 3: In a log-rank 2-sided test with an alpha risk of 0.05, and assuming a 20% dropout rate, the number of patients available would provide >90% power to detect as significant a \geq 20% excess risk (HR \geq 1.20) for any clinical event with a cumulative incidence of \geq 2% in 2 years follow-up. Less common adverse events or weaker associations would require bigger numbers (Table 1).

Table 1. Number of eligible bisphosphonate users needed to ensure 90% statistical power to			
detect as significant the described associations in a 2-sided survival model (log-rank test),			
assuming 5 bisphosphonate non-users will be matched to each user.			

2-year cumulative					
incidence of adverse					
event/s	HR 1.1	HR 1.2	HR 1.3	HR 1.4	HR 1.5
0.50%	330,529	86,234	39,840	23,218	15,353
1%	165,288	43,130	19,929	11,617	7,683
2%	82,667	21,578	9,974	5,817	3,849
3%	55,217	14,394	6,657	3,883	2,570
4%	41,357	10,802	4,997	2,917	1,932
NOTE : cells in bold indicate characteristics of associations we would have 90% power					
to detect					

The incidence of each of the identified adverse events amongst bisphosphonate users is as follows:

- a) Upper gastro-intestinal events: according to data from the pivotal randomized trial for oral alendronate, 11% of the patients allocated to the active treatment arm developed upper gastro-intestinal events, with 1.6% developing serious events (perforation/ulcer/bleeding) (31);
- b) Hypocalcaemia/hypophosphatemia: although the incidence of bisphosphonateinduced hypocalcaemia/hypophosphatemia in the target population (stage ≥3 CKD

patients) is unknown, data from the UK Renal Registry 2013 report suggest that hypocalcaemia and hypophosphatemia are relatively frequent in end-stage renal disease, with a prevalence of 11% and 12% amongst patients on haemodialysis respectively. In addition, data from cancer patients suggest that 8% of them develop hypocalcaemia requiring medical attention following an infusion of intravenous zoledronic acid (13);

c) Acute kidney injury (AKI): the population-based incidence of AKI has been estimated at 209 cases per million person-years (32), therefore making a 2-year cumulative incidence of 0.04%. Therefore, the available sample size would ensure power to detect as significant an excess risk of ≥40% (HR ≥1.4) of AKI associated with bisphosphonate use. It is however well known that the risk of AKI is higher amongst patients with previous CKD (33).

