In summary, the proposed study would have \geq 90% power to detect as significant an excess risk of \geq 10% between bisphosphonate use and both upper GI and hypocalcaemia/hypophosphatemia events, and of (in the most conservative scenario) \geq 40% between use of bisphosphonates and risk of AKI.

Work-package 4: The Danish OUHD included 35,025 patients in the year 2012. We expect to identify at least 500 CKD patients defined as oral bisphosphonate users, matched 1:5 to 2,500 non-users. Accepting type I error of 5% in a two-sided test, and a common mean (standard deviation) hip BMD loss of 0.61% (1.23%) per year (34), this sample size would provide >80% power to detect as significant a >25% difference in bone loss change between bisphosphonate users and non-users.

DATA COLLECTION

Data linkage and management: As stated above, one key advantage of routinely collected data is the immediate access to large and representative samples of patients with no need for prospective data collection. In our proposal, over 200,000 eligible patients (with an eGFR<45) have been identified in CPRD, with >34,000 of them starting bisphosphonate use in the study period.

More challenging is however the workload involved in the linkage and data management required for the current study, where 2 different data sources (CPRD and HES) will be linked to answer the aims of WP1-3. For this reason we have included co-applicants with extensive experience in linkage between these data sources as described above (see "Response to feedback points"). The data management needed to produce a final working dataset will be carried out by a senior data manager at Oxford with expertise in such procedures. With supervision from the PI and the appointed statistician, she will develop ad-hoc code in Python and SQL to produce a dataset that can be analyzed using standard statistical packages such as Stata.

For WP4, investigators at the Odense Patient Data Exploratory Network (OPEN) initiative will carry out the linkage of clinical (including bone mineral density), biochemistry (i.e. serum

creatinine), and pharmacy dispensations data, as well the needed data management. The funding for these are either included in the requested data license fee (linkage and data management) or provided at no cost by external collaborators (supervision by [name] and [name]).

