Sensitivity analyses: Three pre-defined interactions will be tested for, and if significant, stratified analyses will be reported: 1.by gender; 2.by history of previous fracture; and 3.by CKD stage.

In addition, a sensitivity analysis will be carried out to test whether the observed association/s between bisphosphonate use and each of the outcomes follows a gradient, one of the Bradford-Hill criteria of causality (46). To do this, bisphosphonate users will be categorized according to their medication possession ratio (MPR). MPR is calculated as the number of defined daily doses prescribed over the total number of days of follow-up, and it is therefore an approximation of adherence in CPRD and similar datasets.

Bisphosphonate users will then be grouped into: low adherence (MPR <0.4), intermediate adherence (MPR 0.4 to <0.8) and high adherence (MPR \ge 0.8), and HRs will be estimated for each of these categories when compared with matched bisphosphonate non-users.

A post-hoc analysis has been proposed to study the association between bisphosphonate use and hypocalcaemia/hypophosphataemia: given the low number of study participants with the proposed outcome of interest (hospital admission for calcium/phosphate alterations), data has been extracted on laboratory values of serum calcium and phosphate as available in primary care records (CPRD). Hypocalcaemia/hypophosphataemia as defined by these values will be analysed as a secondary outcome for WP3 in addition to the proposed main outcome.

DISSEMINATION AND PROJECTED OUTPUTS

OUTPUTS

A detailed report of our study, including all the work undertaken, will be published in the NIHR HTA Journal. A number of research papers will also be published to report key findings in national and international scientific journals including the Lancet, the British Medical Journal, the Journal of Bone and Mineral Research, Osteoporosis International, Journal of the American Society of Nephrology, or Kidney International, amongst others. Where available, we will publish our findings in open access, and we have requested funding to cover related fees, which range from £1,800 (Osteoporosis International) to £3,000 (BMJ).

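### At the protocol's own 0.04% AKI incidence, power for HR 1.4 is about 18–22%, not the stated 90% or more; the 10% claim for hypocalcaemia/hypophosphataemia does not fit its admission outcome

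*Protocol*

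**What the plan says.** The Work-package 3 paragraph (Protocol, Sampling, Sample size/power) sets the test: "In a log-rank 2-sided test with an alpha risk of 0.05, and assuming a 20% dropout rate". Table 1 is titled "Number of eligible bisphosphonate users needed to ensure 90% statistical power to" detect given hazard ratios with five matched non-users per user. Its lowest incidence row is 0.50%, where HR 1.4 needs 23,218 users. The same section counts 34,127 users among 204,528 eligible patients.

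Item c) starts from a literature rate: "the population-based incidence of AKI has been estimated at 209 cases per million person-years", "therefore making a 2-year cumulative incidence of 0.04" per cent. The next sentence draws the conclusion: "the available sample size would ensure power to detect as significant an excess risk of ≥40% (HR ≥1.4) of AKI". A closing remark says that AKI risk is higher in people who already have CKD, without a rate.

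The Work-package 3 summary claims at least 90% power for an excess of 10% or more in "both upper GI and hypocalcaemia/hypophosphatemia events, and of (in the most conservative scenario") 40% or more for AKI. The planning figures behind the first part are 11% for upper GI events in the alendronate trial, 11% and 12% prevalence of low calcium and low phosphate on haemodialysis, and 8% hypocalcaemia after intravenous zoledronic acid in cancer patients. The Summary of Research restricts the calcium/phosphate outcome to events needing hospital admission. The Sensitivity analyses paragraph later adds a laboratory-based outcome, "given the low number of study participants with the proposed outcome of interest (hospital admission for calcium/phosphate alterations").

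**The concern.** The AKI sentence is presented as following from the 0.04% incidence, yet that incidence is about one twelfth of the lowest row of the table used for every other claim. HR 1.4 is what the 0.50% row supports: 23,218 users suffice there, while HR 1.3 would need 39,840. The claim therefore seems to belong to a different incidence from the one just derived.

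AKI is a central safety outcome for drugs whose use is restricted on renal grounds, and the results are to go to regulators and to NICE. A power statement that is wrong at its own input would give a null AKI finding more weight than the planning figures allow. The same applies, to a lesser degree, to the calcium/phosphate claim, where the incidences used belong to other events and other populations.

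**Working it through.** **Inputs, all from the Protocol's Sample size/power section.** Two-sided log-rank test, alpha 0.05; power 90%; five non-users per user, so the user share is 1/6; 34,127 users, or 27,302 after 20% attrition; AKI rate 209 per million person-years; HR 1.4. (The Summary of Research prints 4,127 users. I use 34,127, which matches the stated 16.7% of 204,528. With 4,127, AKI power would be about 6%.)

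**Step 1: the incidence.** 2 × 209/1,000,000 = 0.0418%. The stated 0.04% is right.

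**Step 2: reproduce Table 1.** A two-proportion calculation (0.5% against 0.7%, ratio 1:5, 90% power) gives about 18,308 users. Dividing by 0.8 for dropout gives about 22,885, against 23,218 printed. The table therefore appears to include the 20% dropout already, and its entries should be compared with 34,127, not 27,302.

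**Step 3: scale Table 1 to AKI.** Required users are inversely proportional to incidence (HR 1.4: 23,218 at 0.50%, 11,617 at 1%).

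- At 0.0418%: 23,218 × 0.50/0.0418 ≈ 277,700 users. 277,700/34,127 ≈ 8.1.
- Incidence at which 34,127 users suffice for HR 1.4: 23,218 × 0.50%/34,127 ≈ 0.34%.

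**Step 4: direct check with Schoenfeld's formula.** Events needed = (1.960 + 1.282)² / [(1/6)(5/6)(ln HR)²]. For HR 1.4, ln HR = 0.3365, so events needed ≈ 668. With incidence p in non-users, expected events = users × p × (1.4 + 5).

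| Users | p | Events | Power for HR 1.4 |
|---|---|---|---|
| 34,127 | 0.0418% | 91 | 22% |
| 34,127 | 0.04% | 87 | 22% |
| 27,302 | 0.0418% | 73 | 19% |
| 27,302 | 0.04% | 70 | 18% |

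Placing the incidence in users or overall, or using a two-proportion test, gives 14–29% two-sided. A one-sided test reaches only about 33%.

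**Step 5: what is detectable.** Solve users × p × (HR + 5) = events needed, at p = 0.04%.

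- 34,127 users: HR ≈ 2.38 (about 101 events expected and needed).
- 27,302 users: HR ≈ 2.60 (about 83 events).
- At 0.0418% the values are 2.34 and 2.55.

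For HR 1.4 at 90% power, p must be 668/(34,127 × 6.4) = 0.31%, or 668/(27,302 × 6.4) = 0.38% after attrition.

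**Step 6: the 10% excess claim.** For HR 1.1, Schoenfeld needs about 8,328 events. The required incidence is 8,328/(34,127 × 6.1) = 4.0%, or 8,328/(27,302 × 6.1) = 5.0% after attrition. Table 1 gives 41,357 × 4%/34,127 = 4.8%. So HR 1.1 needs a 2-year incidence of about 4–5%.

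- Upper GI events at 11%: Table 1 scaling needs 41,357 × 4/11 ≈ 15,000 users. Power exceeds 99% with or without attrition, so the claim holds.
- Calcium/phosphate at 8%: 41,357 × 4/8 ≈ 20,700 users, so the arithmetic also works at that figure. But the figure is not an incidence of hospital admission in patients with eGFR below 45. Item b) calls the target-population incidence of the bisphosphonate-induced disturbance unknown, and the Sensitivity analyses paragraph reports few admissions.

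**The case against.** The strongest defence is that 0.04% is a general-population rate, everyone in this cohort has eGFR below 45, and the Protocol says at once that AKI is commoner in CKD. If the true 2-year incidence is 0.3–0.4% or more, HR 1.4 is detectable after all. That is plausible, and it limits what can be said: a reader might infer that the study is in fact incapable of detecting a 40% excess in AKI, and the documents do not support that, because the cohort's incidence is not given. The defence does not rescue the text, however. The claim is drawn from 0.04% and labelled "in the most conservative scenario", so it has to hold at 0.04%.

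A reader might also infer that the upper GI claim fails, because serious events are put at 1.6%, where power for HR 1.1 would be only 45–54%. The Protocol does not restrict the outcome to serious events; both the Summary of Research and the Aims name upper gastro-intestinal events without that qualifier, and 11% is the figure given for them.

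Two further points stand in the plan's favour. Hazard ratios will be reported with 95% confidence intervals, which will show the AKI precision actually achieved, so misreading of a null result is a risk and not a certainty. And the shortage of calcium/phosphate admissions is acknowledged and partly met by the added laboratory outcome.

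**Conclusion.** The AKI power statement is wrong as written. At the Protocol's own incidence, power for HR 1.4 is about 18–22% instead of 90% or more. The shortfall is about 8-fold in users by Table 1 scaling, and about 7- to 10-fold in incidence (0.31–0.38% needed against 0.04%). It is not a tenfold error in the power figure itself. A wrong table row or a misplaced decimal would explain it, but that is conjecture.

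The result rests on 34,127 users, full 1:5 matching, two years of follow-up and proportional hazards; no two-sided variant tried comes above 29%. The detectable hazard ratio of 2.3–2.6 is approximate, since it relies on a large-sample formula with about 80–100 events.

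The secondary point is narrower: the 10% claim for hypocalcaemia/hypophosphataemia is arithmetically sound at 8–12% but cannot be applied to the admission outcome. Power for that outcome cannot be computed from the document. The upper GI claim stands.

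**What to change.** In Work-package 3, item c), replace the AKI conclusion with wording such as: *At the general-population incidence of 0.04% over two years, the hazard ratio detectable with 90% power is about 2.3 to 2.6. HR 1.4 would be detectable only if the 2-year AKI incidence in patients with eGFR<45 is at least about 0.3–0.4%.* Keep the remark that AKI risk is higher in CKD, and add a rate if the investigators have one.

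In the Work-package 3 summary:

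- Delete the label "in the most conservative scenario" and carry over the conditional AKI statement.
- Keep the 10% claim for upper GI events at the 11% figure.
- For hypocalcaemia/hypophosphataemia, say that a 10% excess is detectable only at a 2-year incidence of about 4–5% or more, and that this is not claimed for the hospital-admission outcome, whose incidence is unknown.

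The cost is protocol wording. Sample, design and analysis are unchanged; the stated detectable effect for AKI becomes much less favourable.

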Confounders: pre-defined lists of confounders will be identified for each of the study outcomes. These will be included in separate propensity score logistic equations to minimize confounding by indication. Propensity scores (ps) represent the probability that a patient will receive a specific treatment based on his/her baseline characteristics (5).

Power: according to feasibility counts from CPRD, 4,127 eligible (eGFR<45) bisphosphonate users and 204,528 eligible non-users are available. These numbers provide >90% power to detect as significant a HR of \geq 1.20 for the association between bisphosphonate use and the outcomes in WP1 and WP3, and a HR o \leq 0.85 for the association between bisphosphonate use and fracture risk (WP2). Regarding WP4, the numbers provided by OUHD (>500 bisphosphonate users and >3,000 non-users with eGFR<45 available in the dataset at 31/12/2012) ensure 80% power to detect as significant an expected >25% difference in bone loss between bisphosphonate users and non-users.

Statistical analyses: firstly, logistic equations will be fitted to estimate ps for each of the study outcomes. Secondly, each bisphosphonate user will be ps-matched to 5 non-users using caliper-matching methods. Ps-matching has been shown to be useful to minimize confounding by indication in observational studies involving drugs (i.e.pharmacoepidemiology) (6). Missing confounders will be handle with 10 multiple imputation by chained equations. Finally, time-varying Cox regression models stratified by ps matched sets will be used to study the association between bisphosphonate use and each of the study outcomes in WP1-3; similarly, linear regression modeling will be used to study the relationship between bisphosphonate use and hip bone density change in WP4.

BACKGROUND AND RATIONALE

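### Work-package 4 claims more than 80% power for a 25% difference in bone loss; its own inputs give about 72%

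*Protocol*

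**What the plan says.** The Work-package 4 paragraph (Protocol, Sampling, Sample size/power) expects "at least 500 CKD patients defined as oral bisphosphonate users, matched 1:5 to 2,500 non-users" in the Danish hospital database. It fixes the test with "Accepting type I error of 5% in a two-sided test" and takes "a common mean (standard deviation) hip BMD loss of 0.61% (1.23%) per year" as the planning value. From these it concludes that "this sample size would provide >80% power to detect as significant a >25% difference in bone loss change" between users and non-users.

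The Summary of Research, under Power, repeats the claim with a slightly different count. It cites ">500 bisphosphonate users and >3,000 non-users with eGFR<45 available in the dataset" and says that these numbers "ensure 80% power to detect as significant an expected >25% difference in bone loss between bisphosphonate users and non-users".

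For the analysis, Beta coefficients (Data analysis) plans linear regression of the change in BMD between two observed time points. The Work-package 4 paragraph states no correlation within matched sets, no reduction in variance from covariates and no allowance for attrition. Work-packages 1 to 3 each allow 20%.

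**The concern.** The power figure can be checked completely from numbers printed beside it, and it does not follow from them. The gap is about 8 percentage points, too large for rounding.

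BMD change is the only outcome of Work-package 4, and the Summary describes a difference above 25% as the expected one. If the true difference sits at that threshold, the study misses it about 28 times in 100, whereas the text promises fewer than 20. Anyone weighing a non-significant BMD result against the stated power would give it more weight than the design supports.

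**Working it through.** **Inputs** (all from the Work-package 4 paragraph unless noted)

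- Two-sided α = 0.05, so the critical value is 1.960
- Users n₁ = 500; non-users n₂ = 2,500 (the Summary gives more than 3,000 available)
- Mean loss 0.61% per year; SD 1.23% per year, common to both groups
- Difference: 25% of the mean loss

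**The plan's figure, recomputed**

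1. Difference δ = 0.25 × 0.61 = 0.1525 percentage points per year (0.1525 / 1.23 = 0.124 SD).
2. Standard error = 1.23 × √(1/500 + 1/2,500) = 1.23 × √0.0024 = 0.0603.
3. δ / SE = 0.1525 / 0.06026 = 2.531.
4. Power = Φ(2.531 − 1.960) = Φ(0.571) = **71.6%**. The exact noncentral t calculation also gives 71.6%.

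The stated figure of more than 80% is not reproduced.

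**Other readings that might produce it**

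| Reading | δ / SE | Power |
|---|---|---|
| 500 : 2,500, two-sided 5% (as written) | 2.531 | 71.6% |
| 500 : 3,000, two-sided 5% (Summary count) | 0.1525 / 0.0594 = 2.567 | 72.8% |
| 500 users, unlimited non-users, two-sided 5% | 0.1525 / 0.0550 = 2.772 | 79.2% |
| 500 : 2,500, one-sided 5% (critical value 1.645) | 2.531 | 81.2% |
| 500 : 2,500, non-users lose 0.61 / 0.75 = 0.813% | 0.2033 / 0.0603 = 3.375 | 92.1% |

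Only the one-sided test lands just above 80%. It may be where the figure came from, but that is an inference, and the paragraph says two-sided.

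**What the design does support**

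- Difference detectable with 80% power at 500 : 2,500: (1.960 + 0.842) × 0.06026 = 0.169 points per year, and 0.169 / 0.61 = **27.7%**.
- Users needed for 80% power at 25%, matched 1:5: 2.802² × 1.23² × 1.2 / 0.1525² = **613**, with 5 × 613 = 3,065 non-users. That is about 23% more than planned.

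**Attrition.** If Work-package 4 lost the 20% allowed in the other work-packages (my assumption; nothing is stated for this one), 400 : 2,000 would remain. The standard error becomes 1.23 × √(1/400 + 1/2,000) = 0.0674, the ratio 0.1525 / 0.0674 = 2.264, and the power Φ(0.304) = 61.9%.

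**The case against.** The arithmetic itself is hard to dispute. The strongest reply is about how the text should be read and how much the error matters.

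- **The text uses inequalities.** It says at least 500 users and a difference above 25%. With 600 : 3,000 the power at 25% would be 79.2%, and with 500 : 2,500 the power at a 30% difference is 85.9%. This softens the error without removing it. A power claim has to hold at the threshold it names, it is made for the stated sample, and 600 users still fall short.
- **The groups are matched.** For 1:5 sets with correlation ρ, the standard error shrinks by √(1 − ρ), so 80% needs (0.0544 / 0.0603)² = 0.816, or ρ of about 0.18. No such correlation is stated, and the planned analysis is described simply as linear regression. If the sponsor relied on one, it should appear among the inputs.
- **The base of the 25% is not spelled out.** Taking 0.61% as the users' loss gives 92.1%. With 0.61% given as a common mean, 25% of 0.61 is the natural reading.
- **Little depends on the figure.** All eligible patients are to be included without recruitment, so the power statement sets no enrolment target and changes no analysis. Work-packages 1 to 3 are unaffected. The BMD effect will be reported with a 95% confidence interval, which is the better guide to a null result. A true effect well above 25% would be found easily: at 50% the power is 99.9%.

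The last point stands. It limits the consequences, and over-reading of a null result is a risk, not a certainty. It does not make the stated figure correct.

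**Conclusion.** The claim is wrong as written in both places. Under the Protocol's own inputs the power at a 25% difference is 71.6%, or 72.8% with 3,000 non-users. The risk of a false negative there is about 28%, against the implied figure of at most 20%. With 500 users and a two-sided 5% test, 80% at 25% is out of reach whatever the number of non-users.

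This rests on independent groups, a common SD of 1.23% and 25% taken of 0.61%, as the text indicates. Any loss of users to matching or to a missing second scan would lower the power further. The error concerns a stated operating characteristic; the design and analysis of Work-package 4 remain usable.

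**What to change.** Correct the sentence in the Work-package 4 paragraph and the matching one in the Summary of Research. Suggested wording:

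> With 500 users and 2,500 non-users, the comparison has about 72% power for a 25% difference in annual bone loss, and 80% power for a difference of about 28% (0.17 percentage points per year).

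Use the same counts in both places. The pool of more than 3,000 available non-users should not be presented as the analysed number when 1:5 matching of 500 users takes 2,500. If the sponsor relied on correlation within matched sets or on variance reduction from covariates, state the value and its source and give the power that follows. Once the data are extracted, report the detectable difference for the number of matched users who actually have two BMD measurements.

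The cost is two sentences of protocol wording and one recalculation. Patients, data collection and the planned analysis do not change.
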